6.7. End of Study Treatment Assessments

Subjects will be removed from study treatment when any of the criteria listed in Section 6.8 apply.

The following procedures will be conducted when a subject goes off study treatment and prior to initiating a new regimen.

If the subject chooses not to continue participation on the study, the procedures listed below are to be conducted within 14 days of the last dose of study treatment or prior to initiating a new therapy.

- Review prior/concomitant medication
- Record any adverse events
- Performance status (ECOG)
- Modified physical exam including weight
- Vital signs; including blood pressure, respiratory rate, pulse, temperature, oxygen saturation level
- Laboratory assessments (Section 6.2.6.):
 - Chemistry
 - Hematology
 - Coagulation
 - Biomarker sampling
- Obtain bone marrow aspirate/biopsy samples for disease assessment and Biomarker testing
- CT scan or PET-CT of affected site/s for subjects with EMD only and without measureable BM involvement unless imaging was performed within 30 days of end of treatment (Patients with no BM involvement and only EMD will not require BM aspirate/biopsy)

6.7.1. **30-Day Follow-up**

After the last dose of study drug, subjects should be followed for any drug-related AEs and/or ongoing serious adverse events (SAEs) until those events have resolved or become stable, whichever occurs later. The site will contact the study subject regardless of AE/SAE status approximately 30 days after the subject's last dose of study drug to assess adverse events since the last study visit and review concomitant medications. Subject should be contacted by phone (or in person, if necessary) to assess the subject's condition and record any adverse events reported during the follow-up contact. Phone call or visit should be documented.

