7.2.2. Assessment of Severity

The severity of adverse events will be graded using the CTCAE, Version 4.03. For each episode, the highest severity grade attained should be reported.

If a CTCAE criterion does not exist, the investigator should use the grade or adjectives: Grade 1 (mild), Grade 2 (moderate), Grade 3 (severe), Grade 4 (life-threatening), or Grade 5 (fatal) to describe the maximum intensity of the adverse event. For purposes of consistency with the CTCAE, these intensity grades are defined in Table 7-1.

Grade	Adjective	Description
Grade 1	Mild	Sign or symptom is present, but it is easily tolerated, is not expected to have a clinically significant effect on the subject's overall health and well-being, does not interfere with the subject's usual function, and is not likely to require medical attention.
Grade 2	Moderate	Sign or symptom causes interference with usual activity or affect clinical status, and may require medical intervention.
Grade 3	Severe	Sign or symptom is incapacitating or significantly affects clinical status and likely requires medical intervention and/or close follow-up.
Grade 4	Life-threatening	Sign or symptom results in a potential threat to life.
Grade 5	Fatal	Sign or symptom results in death.

Table 7-1.Grading of Adverse Event Severity

The distinction between the seriousness and the severity of an adverse event should be noted. Severe is a measure of intensity; thus, a severe reaction is not necessarily a serious reaction. For example, a headache may be severe in intensity, but would not be classified as serious unless it met one of the criteria for serious events listed in Section 7.3.

7.3. Investigator Requirements and Instructions for Reporting Adverse Events and Serious Adverse Events to Gilead

Requirements for collection prior to study drug initiation:

After informed consent, but prior to initiation of study medication, the following types of events should be reported on the case report form (CRF/eCRF): all SAEs and adverse events related to protocol-mandated procedures.

Adverse Events

Following initiation of study medication until 30 days after last administration of study medication AEs, regardless of cause or relationship, must be reported to the CRF/eCRF database as instructed.

All AEs should be followed up until resolution or until the adverse event is stable, if possible. Gilead Sciences may request that certain AEs be followed beyond the protocol defined follow up period.

Serious Adverse Events

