All SAEs, regardless of cause or relationship, that occurs after the subject first consents to participate in the study (ie, signing the informed consent) and throughout the duration of the study, including the protocol-required post treatment follow-up period, must be reported to the CRF/eCRF database and Gilead Drug Safety and Public Health (DSPH) as instructed. This also includes any SAEs resulting from protocol-associated procedures performed after informed consent is signed.

Any SAEs and deaths that occur after the post treatment follow-up visit but within 30-days of the last dose of study drug, regardless of causality, should also be reported.

Investigators are not obligated to actively seek SAEs after the protocol defined follow up period however, if the investigator learns of any SAEs that occur after study participation has concluded and the event is deemed relevant to the use of study drug, he/she should promptly document and report the event to Gilead DSPH.

• All AEs and SAEs will be recorded in the CRF/eCRF database within the timelines outlined in the CRF/eCRF completion guideline.

Electronic Serious Adverse Event (eSAE) Reporting Process

- Site personnel record all SAE data in the eCRF database and from there transmit the SAE information to Gilead DSPH within 24 hours of the investigator's knowledge of the event. Detailed instructions can be found in the eCRF completion guidelines.
- If for any reason it is not possible to record the SAE information electronically, ie, the eCRF database is not functioning, record the SAE on the paper serious adverse event reporting form and submit within 24 hours to: Email: PPD and Fax: PPD
- As soon as it is possible to do so, any SAE reported via paper must be transcribed into the eCRF Database according to instructions in the eCRF completion guidelines.
- If an SAE has been reported via a paper form because the eCRF database has been locked, no further action is necessary. For fatal or life-threatening events, copies of hospital case reports, autopsy reports, and other documents are also to be submitted by e-mail or fax when requested and applicable. Transmission of such documents should occur without personal subject identification, maintaining the traceability of a document to the subject identifiers.
- Additional information may be requested to ensure the timely completion of accurate safety reports.

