8.6.2. Adverse Events

All adverse events will be listed. The focus of adverse event summarization will be on treatment emergent adverse events. A treatment-emergent adverse event is defined as an adverse event that onset in the period from the first dose of study treatment to 30 days after the permanent discontinuation of study treatment or that leads to permanent discontinuation of study treatment. Adverse events that occur before the first dose of study treatment or >30 days after the subject has been discontinued from study treatment will be included in data listings.

Adverse events will be classified using MedDRA (http://www.meddramsso.com) with descriptions by System Organ Class, High-Level Group Term, High Level Term, Preferred Term, and Lower-Level Term. The severity of adverse events will be graded by the investigator according to the CTCAE, Version 4.03 (http://evs.nci.nih.gov/ftp1/CTCAE/CTCAE_4.03_2010-06-14_QuickReference_5x7.pdf), whenever possible. If a CTCAE criterion does not exist for a specific type of adverse event, the grade corresponding to the appropriate adjective will be used by the investigator to describe the maximum intensity of the adverse event: Grade 1 (mild), Grade 2 (moderate), Grade 3 (severe), Grade 4 (life threatening), or Grade 5 (fatal). The relationship of the adverse event to the study treatment will be categorized as related or unrelated.

Treatment-emergent adverse events will be summarized. Summary tables will be presented to show the number of subjects reporting treatment-emergent adverse events by severity grade and corresponding percentages. A subject who reports multiple treatment-emergent adverse events within the same Preferred Term (or System Organ Class) is counted only once for that Preferred Term (or System Organ Class) using the worst severity grade. The summary will be presented in decreasing frequency of System Organ Class and Preferred Term of the 'Total' column. Within the same frequency, the AEs are ordered in the alphabetical order of System Organ Class and Preferred Term.

Separate listings and summaries will be prepared for the following types of treatment emergent adverse events:

- Study-drug-related adverse events
- Adverse events that are Grade \geq 3 in severity
- Adverse events leading to study treatment interruption and/or dose modification
- Adverse events leading to study treatment discontinuation
- Serious adverse events

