7.1.5. Treatment-Emergent Adverse Events

7.1.5.1. Definition of Treatment-Emergent Adverse Events

AEs which meet at least one of the following criteria are defined as Treatment-Emergent Adverse Events (TEAEs):

- Any AEs with onset dates on or after the start of study treatment and up to 30 days after the permanent discontinuation of the study treatment
- Any AEs leading to permanent discontinuation of study treatment

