- c Following consent, adverse events will be assessed pre-and post-dose during each clinic visit, and 30 (±7) days following completion of the subject's last dose of study drug. Subjects should be contacted by phone (or in person, if necessary) 30 days (±7 days) after the subject's last dose of study drug to assess AEs. Subjects should be asked specifically if there are any AEs since stopping the study.
- d Bone marrow aspirate/biopsy will be taken during Screening; Cycle 1 on Day 8 and Day 28; Cycle 2 on Day 28. PPD
- e CBC with differential including PT/INR and PTT.
- f For female subjects of childbearing potential, serum testing performed at screening only. Urine pregnancy test will be performed at Lead-in on Day -7 of (escalation) or during Cycle 1 on Day 1 (expansion). Pregnancy tests will be performed on a Day 1 of each cycle thereafter.
- g Pharmacokinetic peripheral blood samples will be obtained pre-dose during Lead-in on Day -7; Cycle 1 on Day 1, 8, 28 and Cycle 2 on Day 28. PK blood samples will also be collected 1.5 hours post-dose of ENTO (±30 minutes) during Lead-in on Day -7; Cycle 1 on Days 1, 8, 28 and Cycle 2 on Day 28. CNS prophylaxis administration is independent of PK time point.

h CSF samples will be collected for pharmacokinetic analysis during Cycles 1 and Cycle 2 on Day 28 (prior to CNS prophylaxis administration).

PPD

PPD

k Subjects with EMD only, with no BM involvement will not require BM aspirate/biopsy

l Treatment with ENTO will be continuous. ENTO should be dispensed on Day 28 to include cycle break drug coverage, if necessary.

m Vincristine will be administered during Cycles 1 and Cycle 2 on Days 1, 8, 15, 22 and during Maintenance on Day 1 of each cycle.

n Dexamethasone (20 mg BID; dosed for 4 days) will be dispensed during Cycle 1 on Day 8 and Day 22 and during Cycle 2 on Day 1 and Day 15. During Maintenance, dexamethasone (20 mg QD or 10 mg BID; dosed for 4 days) will be dispensed on Day 1 and Day 15 of each cycle.

o CNS prophylaxis per institutional standard during Cycle 1 and Cycle 2 on Day 28 (± 3 days).

SAP CSR GS-US-339-1560_v1.0

ELECTRONIC SIGNATURES

Signed by	Meaning of Signature	Server Date (dd-MMM- yyyy hh:mm:ss)
PPD	Clinical Research eSigned	11-Jan-2019 00:43:50
PPD	Biostatistics eSigned	11-Jan-2019 01:19:08

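### The last scheduled AE enquiry may be made on day 23 after the last dose, so new non-serious AEs on days 24 to 30, although reportable and treatment-emergent, may never be asked about

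*SAP*

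**What the plan says.** Four provisions bear on this point.

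- **Reporting period.** Protocol 7.3 states: "Following initiation of study medication until 30 days after last administration of study medication AEs, regardless of cause or relationship, must be reported".
- **Analysis period.** SAP 7.1.5.1 counts AEs with onset "up to 30 days after the permanent discontinuation of the study treatment" as treatment-emergent. Protocol 8.6.2 has the same limit, "30 days after the permanent discontinuation of study treatment".
- **Enquiry.** Footnote c of SAP Appendix 1, which repeats footnote c of Protocol Appendix 2, places the follow-up contact at "30 days (±7 days) after the subject's last dose of study drug to assess AEs". The footnote gives the ±7-day tolerance twice, and adds that subjects should be asked specifically about AEs. Protocol 6.7.1 gives no tolerance: the site makes contact "approximately 30 days after the subject's last dose of study drug to assess adverse events since the last study visit".
- **Events after the contact.** Protocol 7.3 also asks for reports of "Any SAEs and deaths that occur after the post treatment follow-up visit but within 30-days of the last dose of study drug". Non-serious AEs are not mentioned there.

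Two other contacts surround this one. The end-of-treatment assessments in Protocol 6.7 record AEs when the subject goes off treatment. For subjects who leave the study they are due "within 14 days of the last dose of study treatment or prior to initiating a new therapy". Long-term follow-up (Protocol 6.7.2) takes place every 3 months and lists ALL treatments, other malignancies and survival as its content, with no AE item.

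**The concern.** The enquiry window is symmetric about day 30, while the reporting and treatment-emergent windows end at day 30. A site that calls on day 23 complies fully, yet its call looks back only to the last visit and cannot cover days 24 to 30. The protocol foresees that the visit may come before day 30, because it adds a clause for later SAEs and deaths, but nothing comparable prompts for non-serious events, which include Grade 3 or 4 events that do not meet a seriousness criterion.

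At stake is the completeness of the treatment-emergent AE tables in a study whose primary objective is safety. Any loss runs in one direction, towards under-counting. Its size for a given subject would depend on when the site happened to call, not on anything clinical.

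**Working it through.** The plan gives no figure for this gap to reproduce; the check is arithmetic on the windows.

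**Inputs**
- Contact: 30 ± 7 days after the last dose (footnote c, both schedules).
- End of AE reporting: day 30 after the last administration (Protocol 7.3).
- End of treatment-emergent window: day 30 after permanent discontinuation (Protocol 8.6.2, SAP 7.1.5.1). For the arithmetic, both clocks are taken to start on the same date.

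**Permitted range.** Earliest contact 30 − 7 = day 23; latest 30 + 7 = day 37. That is 15 whole days.

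**Days left unasked after a contact on day d.** Gap(d) = max(0, 30 − d).

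| Contact day | 23 | 24 | 25 | 26 | 27 | 28 | 29 | 30 to 37 |
|---|---|---|---|---|---|---|---|---|
| Days unasked | 7 | 6 | 5 | 4 | 3 | 2 | 1 | 0 |

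**Extreme.** 7/30 = 23.3% of the post-treatment window.

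**Illustrative average.** Assume that contacts fall evenly on the 15 whole days. The documents do not say this.
- Share before day 30: 7/15 = 47%.
- Mean gap: (7 + 6 + 5 + 4 + 3 + 2 + 1)/15 = 28/15 = 1.87 days.
- As a share of the post-treatment window: 1.87/30 = 6.2%.

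**Against the whole treatment-emergent window.** This window starts at first dose. A subject who completes the lead-in and both induction cycles with no break has 7 + 28 + 28 = 63 treatment days, plus 30, so 93 days. The mean gap is then 1.87/93 = 2.0% and the extreme 7/93 = 7.5%. The share is larger for subjects who stop earlier and smaller for those in maintenance.

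**Does another contact cover the gap?** The end-of-treatment assessments normally come earlier. Long-term follow-up lists no AE item. Following drug-related AEs and ongoing SAEs until they resolve (Protocol 6.7.1) tracks events already known and does not elicit new ones.

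**After a one-sided window.** For contacts on days 30 to 37, Gap(d) = 0 on every permitted day, provided that both windows start on the same date.

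**Do they start on the same date?** Footnote c counts from the last dose of study drug, which Protocol 6.4.1 and 7.2.1 identify with GS-9973. The treatment-emergent definitions count from permanent discontinuation of study treatment. If study treatment includes vincristine or dexamethasone, and one of them stops after GS-9973, the gap could exceed 7 days. The documents do not settle this.

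**The case against.** The strongest reply is that the contact date does not govern the collection period. Protocol 7.3 sets the duty to report all AEs to day 30, whenever the call is made. This stands. A reader might infer that an early call closes AE collection, but no section says so. What an early call weakens is ascertainment: the duty remains, without a scheduled question to discover the event.

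A reader might also infer that serious events or deaths on days 24 to 30 would be lost. The Protocol 7.3 clause on events after the follow-up visit covers them, and the seriousness criteria in Protocol 7.1.2 bring many of the gravest events under it.

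A third reply is that the primary endpoint in Protocol 8.1.2 is DLTs, assessed in the lead-in and Cycle 1, so escalation decisions are untouched unless treatment stops early within that window. This also stands. The point keeps some relevance because the synopsis also lists AEs and laboratory abnormalities that are not DLTs under the primary safety evaluation.

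Finally, with 3 to 6 subjects per dose level, one subject is 17 to 33 percentage points (1/6 to 1/3), and it is tempting to give that as the effect of the gap. It is arithmetic that applies to any cohort of this size. Subjects are counted once per term, so a missed event changes an incidence only if that subject did not already have the term; a worst-grade table changes only if the missed event was of higher grade. The documents give no basis for a probability of either.

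**Conclusion.** The mismatch is real and small. New non-serious AEs in the last 1 to 7 days of the 30-day post-treatment period remain reportable but may not be asked about when the contact is made on days 23 to 29. The upper bound is 7 of 30 days, assuming that both clocks start together. The average of 1.87 days (6.2%), with 47% of contacts before day 30, rests on evenly spread contact days and is only an illustration. No contact dates are given, so the actual loss is unknown and may be negligible. Any effect on the AE tables is an under-count; DLT assessment is generally unaffected. This is a cheap improvement, not a flaw that threatens the study's conclusions.

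**What to change.** 1. In footnote c of Protocol Appendix 2, mirrored in SAP Appendix 1, change both ±7-day tolerances to +7 days, so that the contact falls on days 30 to 37.
2. In Protocol 6.7.1, replace the approximate timing with no earlier than 30 days.
3. Time the contact from the date that starts the 30-day treatment-emergent window (last dose of study treatment), and say which agents that term includes. Without this step, the one-sided tolerance cannot be said always to cover the window.

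The cost is a narrower scheduling window for one phone call; no visit is added. The benefit is limited to subjects not yet contacted: escalation is complete, expansion closed with no subjects enrolled, and SAP Section 1 describes only the continued treatment or follow-up of subjects already on study. The change to the SAP appendix only keeps it aligned with the protocol and alters no analysis. For subjects already contacted, a listing of the contact day relative to the last dose would show how large the gap actually was.
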